6.4. Visit Windows

Study visits will be defined through the use of windows based on the list of visits described in Section 1.3 of the Protocol. For all assessments, the number of days from baseline will be calculated using the following formula: (date of assessment) - (date of first study treatment) + 1. This number of days will be used to assign analysis visits. This may not always correspond to the eCRF visit.

All post-baseline records including those that occurred outside the specified protocol windows will be assigned to an appropriate analysis visit by using the following scheme and will be included in the analysis of the specific assessment, where applicable.

Generally, the lower bound for each analysis visit window is defined as the midpoint of the target dates between 2 consecutive scheduled visits. The upper bound of the last visit window is set as the target date + 7 days. If the date of assessment falls between the lower and the upper bound for a visit as defined in the schedule of assessments (see Section 1.3 of the protocol), then it will be assigned to that visit. If the interval separating 2 scheduled visits is an even number of days, that middle day will be included in the lower bound of the next visit window.

If only 1 record is within an analysis visit window, the data from that record will be used in the analysis. If more than 1 record is within the same analysis visit window, the record closest to the midpoint of the

This document is confidential.

SAP Version: 2.0 09-Feb-2023

Controlled Document ID: 3903A.02, Effective Date 31-Aug-2020

interval will be used in the analysis. If 2 records are "tied" before and after the middle of the interval, the earlier record will be used in the analysis. Participants who switch to q6w dosing will likely have more than 1 record in some visit windows. The decision rules described above will be applied to the q6w visits to determine which measurements will be used in the analysis.

See Table 2 for visit window definitions.

Table 2: Visit Windows (Days)

Visit	Nominal Day	Visit Window		
Screening Period				
Day -85	-85	-85 – -79		
Day -71	-71	-78 – -65		
Day -57	-57	-64 – -51		
Day -43	-43	-50 – -37		
Day -29	-29	-36 – -23		
Day -15	-15	-22 – -1		
Confirmation Visit				
Day 1	1	1 - 1		
Evaluation Period				
Day 15	15	8 – 42		
Day 71	71	43 – 98		
Day 127	127	99 – 154		
Day 183	183	155 – 210		
Day 239	239	211 – 266		
Day 295	295	267 – 322		
Day 351	351	323 – 378		
Follow-up	407	379 – max		

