#### Table 1: Schedule of Study Visits and Assessments: Screening Visit Through Confirmation Visit

Abbreviations: ADA = antidrug antibody; AE = adverse event; BTH = breakthrough hemolysis; C5 = complement component C5; ECG = electrocardiogram; HIV = human immunodeficiency virus; LDH = lactate dehydrogenase; LDH-PCHG = lactate dehydrogenase percent change; PD = pharmacodynamic; PK = pharmacokinetic; RBC = red blood cell; SAE = serious adverse event; WBC = white blood cell.

Period	Confirmation Visit			Evalu	uation	Period			Unscheduled Visits	Follow- up call	Notes
Study Day	1	15	71	127	183	239	295	351/ ET	NA	407	
Window (day)	NA	± 2	±7	± 7	± 7	± 7	± 7	± 7		± 7	
Inclusion and exclusion criteria	Х										LDH and hematologic criteria assessed
Physical examination	Х							X			
Abbreviated physical examination		X	X	Х	Х	X	Х		Х		Refer to Section 8.2.1 for details
Weight	Х	Х	Х	Х	Х	Х	Х	Х	Х		
Serum or urine pregnancy test	Х	X	X	X	X	X	X	X	Х		Refer to Section 8.3.5 for details. Serum pregnancy test at Day 1, and Day 351/ET.; Urine pregnancy test at all other visits
Chemistry including LDH	Х	X	X	X	Х	X	Х	X	Х		Sample to be collected within 24 hours of or immediately prior to a scheduled dose of study drug (trough) and not from a heparinized line.
Hematology including free hemoglobin and coagulation	Х	X	X	Х	Х	X	Х	X	Х		Blood will be collected predose on dosing days and not from a heparinized line.
Urinalysis and urine chemistry	Х	Х	X	X	X	X	X	X	Х		Urine will be collected predose on dosing days.
Safety 12-lead ECG								X			Refer to Section 8.2.3 for details
Vital signs	Х	X	Х	Х	Х	X	Х	X	Х		Will be measured after the participant has been resting for at least 5 minutes. Refer to Section 8.2.2 for details
PNH clone size	Х			X				X			WBC (granulocyte and monocyte) and RBC clone size measured by high- sensitivity flow cytometry at Day 1; RBC clone size only at Day 127 and Day 351/ET

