### 8.2.4. Clinical Safety Laboratory Assessments

• Detailed instructions on the procedure for collection, processing, storage, and shipment of the samples for laboratory analyses will be provided in the Laboratory Study Manual. All sample analyses will be performed by Alexion or its designee.

- See Section 10.2 for the clinical laboratory tests to be performed and the SoA (Section 1.3) for their timing and frequency.
- If a suspected event of BTH occurs, LDH, PK, and PD samples will be collected and analyzed. If the suspected event of BTH does not occur at a scheduled visit, an unscheduled visit should be conducted for evaluation of the participant and collection of the required LDH, PK, and PD samples.
- The Investigator must review the laboratory report, document this review, and record any clinically relevant changes occurring during the study in the AE section of the eCRF. The laboratory reports must be filed with the source documents. Clinically significant abnormal laboratory findings are those which are not associated with the underlying disease, unless judged by the Investigator to be more severe than expected for the participant's condition.
- All laboratory tests with values considered clinically significantly abnormal during participation in the study should be discussed by the Investigator and Medical Monitor.
  - If such values do not return to normal/baseline within a period of time judged reasonable by the Investigator, the etiology should be identified, and Alexion notified.
  - All protocol-required laboratory assessments, as defined in Section 10.2, must be conducted in accordance with the laboratory manual and the SoA.
  - If laboratory values from non-protocol specified laboratory assessments performed at the institution's local laboratory require a change in participant management or are considered clinically significant by the Investigator (eg, SAE or AE or dose modification), then the results must be recorded in the CRF.

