8.2.2. Hemolysis

Hemolysis is analyzed as directly measured as the percentage change in LDH from baseline.

The percentage change in LDH will be analyzed using a mixed model for repeated measures (MMRM) (Mallinckrodt, 2001; Mallinckrodt, 2004) with the fixed categorical effects of study visit, and the continuous fixed covariate of baseline LDH. Baseline is defined as the average of all assessments analyzed by the central laboratory prior to the first study drug administration. The Kenward-Roger approximation will be used to estimate denominator degrees of freedom. A p-value testing whether percent changes differ from 0 at each visit will be calculated.

Absolute LDH levels, and the change and percent change from baseline, will be summarized at all study visits up to Day 351.

This document is confidential

SAP Version: 2.0 09-Feb-2023

Controlled Document ID: 3903A.02, Effective Date 31-Aug-2020

The number (%) of participants achieving LDH levels at or below ULN (1.0 × ULN) and levels at or below 1.5 × ULN will be displayed.

Mean (±95% CI) of absolute LDH levels, and the change and percent change from baseline will be plotted over time.

All data will be listed.

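### The SAP's closest-to-midpoint rule lets an unscheduled LDH on Days 16–34 replace an on-time Day 15 predose trough

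*SAP*

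**What the plan says.** SAP Section 6.4 sends all data through the windows: "All post-baseline records including those that occurred outside the specified protocol windows will be assigned to an appropriate analysis visit". Assignment is by study day and need not match the eCRF visit. Where a window holds several records, the rule is: "If more than 1 record is within the same analysis visit window, the record closest to the midpoint of the" interval is used, and a tie goes to the earlier record. The only case of multiple records it discusses is participants who switch to q6w dosing. SAP Table 2 gives Day 15 a window of Days 8–42.

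The chemistry row of Protocol Section 1.3, Table 2 has LDH drawn within 24 hours of, or "immediately prior to a scheduled dose of study drug (trough"). Day 15 is a dosing day with a ±2-day visit window. The same row includes LDH at unscheduled visits. For a suspected BTH outside the schedule, Protocol Section 8.2.4 says that "an unscheduled visit should be conducted for evaluation of the participant and collection of the required LDH, PK, and PD samples".

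SAP Section 8.2.2 analyses LDH percent change by visit in an MMRM ("A p-value testing whether percent changes differ from 0 at each visit will be calculated"), summarises LDH at all visits up to Day 351, and adds counts against ULN thresholds ("levels at or below 1.5 × ULN will be displayed").

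On the last window, the text of Section 6.4 says "The upper bound of the last visit window is set as the target date + 7 days". Table 2 shows Day 378 for the Day 351 visit and an open end for Follow-up.

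**The concern.** A nearest-to-midpoint rule is harmless when the nominal day sits in the middle of its window. Day 15 does not: the preceding visit is 14 days earlier and the next is 56 days later, so the window stretches well to the right. The rule then favours samples taken about ten days after the visit over the visit itself.

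The two kinds of sample differ. The scheduled one is a trough before the first maintenance dose. The displacing one is taken 1 to 19 days after that dose and may be event-triggered. Labelled as Day 15, it enters the first post-switch LDH result in the MMRM and the by-visit summaries. In the interim for publication (SAP Section 13: first 10 participants, data through Day 183), Day 15 is one of only four post-baseline LDH visits (15, 71, 127, 183), and one participant carries twice the weight it has among 20.

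**Working it through.** **Reproducing Table 2.** The lower bound is the midpoint between consecutive target days; the upper bound is the day before the next lower bound.

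- Day 15: lower (1 + 15)/2 = 8; next lower bound (15 + 71)/2 = 43, so upper 42. This matches Table 2.
- Day 71: lower 43; next lower bound (71 + 127)/2 = 99, so upper 98. This matches.
- The remaining five windows, up to 323–378 for Day 351, reproduce in the same way.

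**Window midpoints.** Day 15: (8 + 42)/2 = 25, which is 10 days after the nominal day. The other six are 70.5, 126.5, 182.5, 238.5, 294.5 and 350.5, each half a day before the nominal day.

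**Which records displace an on-time visit.** A record on day d wins if it is closer to the midpoint, or tied and earlier.

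- Day 15: |d − 25| < |15 − 25| = 10 gives d = 16 to 34, that is 19 days. Day 35 ties but is later, so it loses.
- Day 71: the on-time record is 0.5 day from 70.5. Only Day 70 beats it (tied and earlier). The other five windows behave alike: 1 day each.

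**Across the permitted Day 15 ± 2 visit dates,** under the SAP rule and under a nearest-to-nominal-day rule with no scheduled-visit preference:

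| Scheduled visit held on | Displacing days, SAP rule | Displacing days, nominal-day rule alone |
|---|---|---|
| Day 13 | 14–36 (23) | 14–16 (3) |
| Day 14 | 15–35 (21) | 15 (1) |
| Day 15 | 16–34 (19) | none |
| Day 16 | 17–33 (17) | 14–15 (2) |
| Day 17 | 18–32 (15) | 13–16 (4) |

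**Size of one displacement (illustration).** Assume that the scheduled Day 15 LDH equals baseline, b × ULN, and that the displacing LDH is 2 × ULN. The mean percent change at Day 15 then moves by (2/b − 1) × 100 / n.

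| Baseline b (× ULN) | n = 20 | n = 10 |
|---|---|---|
| 1.0 | 5.0 points | 10.0 points |
| 1.5 | 1.7 | 3.3 |
| 1.75 | 0.7 | 1.4 |
| 2.0 | 0 | 0 |

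If the count at or below 1.5 × ULN is shown by visit, which Section 8.2.2 does not state, one participant whose scheduled value qualifies and whose displacing value is at least 2 × ULN lowers the Day 15 percentage by 1/20 = 5 points, or 1/10 = 10 points at the interim.

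**Last-window sentence.** 351 + 7 = 358 against 378 in Table 2 if Day 351 is meant; 407 + 7 = 414 against no upper limit if Follow-up is meant. Section 6.4 ends with "See Table 2 for visit window definitions", so the table can be taken to govern, and this is a wording mismatch only.

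**The case against.** The strongest reply is that the reach is small.

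- **Endpoints.** The primary endpoint and the BTH proportion rest on the eCRF BTH form (SAP Sections 8.1 and 8.2.1), not on windowed LDH. The named LDH endpoint is Day 351. The study tests no formal hypotheses, and all LDH values are listed, with individual plots of central-laboratory LDH. This stands and is why the point is minor.
- **Frequency.** The documents give no rate of unscheduled samples on Days 16–34. They may be rare: BTH during Screening makes a participant ineligible, and Protocol Appendix 7 describes inhibitor concentration as relatively high shortly after dosing. This also stands. However, Protocol Table 5 gives guidance for BTH up to 2 weeks, and between 2 and 6 weeks, after a dose, so the plan foresees such events.
- **The contrast of 19 days with 1 is for on-time visits.** Other visits may be held ±7 days from target. A Day 71 visit held on Day 78 can be displaced by Days 63–77 (15 days), and one held on Day 64 by Days 65–76 (12 days). That is correct, and any nearest-record rule without a scheduled-visit preference has this weakness. Only at Day 15 does a punctual visit face a 10-day handicap.
- **Table top hemolysis.** SAP Section 11.2 drops LDH from samples with potassium of at least 6 mmol/L and LDH of at least 2 × ULN. This would remove some displacing values, but only those with high potassium as well.
- **Intent.** The authors may have meant the nominal day. The text says the midpoint of the interval, and a programmer would code that.

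**Conclusion.** The point holds, at minor severity. Read literally, SAP Section 6.4 with Table 2 lets any record on Days 16–34 displace an on-time Day 15 predose record, and nothing elsewhere in the plan prevents it. The range of displacing days is 15 to 23 in number, depending on where in the ±2-day window the visit falls.

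What is affected is the Day 15 LDH estimate, its descriptive p-value and other Day 15 by-visit summaries. With complete data, a Day 15 displacement leaves the Day 351 LDH mean unchanged; a Day 351 record can itself be displaced only in the ordinary way described above. The sizes shown depend on the assumed LDH values and on at least one q8w participant having such a sample. The target + 7 days sentence has no analytic consequence while Table 2 governs.

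**What to change.** In SAP Section 6.4, replace the midpoint rule: where a window contains the scheduled visit for that assessment, use it; otherwise use the record closest to the nominal day, with the earlier one on a tie. Both parts are needed, because the nominal-day rule alone still leaves visits on Days 13, 14, 16 and 17 open to displacement, as the table of visit dates shows. Unscheduled values remain in the listings and on the BTH form.

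Also reword the last-window sentence to agree with Table 2, keeping 323–378 for Day 351.

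The cost is two sentences and a small programming change. No extra data are needed.

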6.5. Pooling of Centers

Pooling of centers is not applicable to this study

6.6. Subgroups

No subgroup analysis is planned because of the small sample size of the study.

This document is confidential.

SAP Version: 2.0 09-Feb-2023

Controlled Document ID: **3903A.02**, Effective Date 31-Aug-2020

7. Participant Disposition, Demographic, Other Baseline Characteristics and Medication

7.1. Participant Disposition and Withdrawals

The number and percentage of participants screened, failed screening, treated, completing treatment, discontinued treatment, reasons for discontinuation of treatment, completing the study, switching to q6w dosing, discontinued from the study, reasons for discontinuation, and those included in each analysis set will be summarized. The number of participants with discontinuation status impacted by COVID-19 will be included in the summary.

Screen failures are defined as participants who consent to participate in the clinical study but are not subsequently entered in the study. Individuals who do not meet the criteria for participation in this study because of a reason that is expected to resolve or has resolved may be rescreened based on discussion and agreement between the Investigator and the Medical Monitor. Rescreened participants will be assigned a new participant identification (ID) number. The ID number of the previous screen failure will be linked to the new participant ID number in the eCRF.

Completion/discontinuation status, inclusion/exclusion criteria definitions, and inclusion/exclusion criteria violations will be listed by participant.

A listing of participants showing their affiliation to the different analysis sets will also be generated.

7.2. Demographic and Baseline Characteristics

Participant demographic and baseline characteristics will be summarized for the FAS. Summary statistics will be presented for the following variables:

- Age at baseline (years)
- Age group at baseline (<65 years, ≥65 years)
- Sex
- Ethnicity
- Race
- Height (cm)
- Weight (kg) at baseline
- Body mass index

All demographic data will be listed.

7.3. Medical History and Concomitant Diseases

Medical history will be classified by System Organ Class (SOC) and Preferred Term (PT) using Medical Dictionary for Regulatory Activities Terminology (MedDRA) version 23.1, and will be summarized for the FAS. Tables will be sorted alphabetically by SOC and descending frequency of PT within SOC. Byparticipant listings of medical history will be presented. The following medical history variables will be summarized:

This document is confidential

SAP Version: 2.0 09-Feb-2023

Controlled Document ID: 3903A.02, Effective Date 31-Aug-2020

- · Relevant medical conditions/surgeries prior to informed consent
- Participants with any condition associated with major adverse vascular event (MAVE)
- Participants with any PNH symptoms experienced at any time prior to informed consent
- Participants with any conditions associated with PNH diagnosed at any time prior to informed consent

7.4. PNH Medical History and Disease Characteristics

PNH medical history will be listed for all participants in the FAS. The following PNH medical history and disease characteristics will be summarized:

- Age at PNH diagnosis, calculated as: year of first PNH-associated diagnosis year of birth
- Method of PNH diagnosis
- Years from PNH diagnosis to informed consent, calculated as: year of first PNH-associated diagnosis – year of informed consent
- Total red blood cell PNH clone size at screening
- Granulocyte clone size at screening
- Monocyte clone size at screening
- Need for packed red blood cell transfusion within 6 months / 1 year prior to the first dose of study drug
- Number of packed red blood cell transfusion episodes within 6 months / 1 year prior to first dose
 of study drug
- Number of units transfused within 6 months / 1 year prior to the first dose of study drug

7.5. Medication and Procedures

Medications will be classified using the World Health Organization Drug Dictionary (WHODrug) version B3 Global September 2020. Medication summaries (ie, number [%] of participants using prior and concomitant medications) will be presented by therapeutic class (Anatomical Therapeutic Chemical [ATC] Level 3) and generic name.

7.5.1. Prior Medication

Prior medications are defined as medications that the participant takes within 28 days prior to the start of screening until the first dose of study drug, eculizumab taken during the 3 months prior to screening, and all meningococcal vaccinations administered within 3 years prior to the first dose of study drug.

Prior medications will be summarized for the FAS. Eculizumab taken prior to screening will be summarized separately to eculizumab taken during the Screening Period. A listing of prior medications, including eculizumab taken prior to screening, will be produced. Eculizumab taken during the screening period will be listed separately. A separate listing of meningococcal vaccinations will be produced showing the date and type of vaccination for each participant.

This document is confidential.

SAP Version: 2.0 09-Feb-2023

Controlled Document ID: 3903A.02, Effective Date 31-Aug-2020

7.5.2. Concomitant Medication

Concomitant medications are defined as medications taken on or after the first infusion of the study drug through 30 days after the participant's last dose of the study drug.

Concomitant medications will be summarized for the FAS. A by-participant listing will also be produced.

7.5.3. Non-Pharmacologic Therapies and Procedures

Non-pharmacologic therapies and procedures will be listed for the FAS.

7.6. Extent of Exposure

Summaries of exposure will consider all infusions of ravulizumab (ie, those given under both the q8w and q6w dosing regimens). Summary statistics (mean, SD, median, minimum, and maximum) will be produced for the following using the Safety Set:

- Number of infusions from Day 1 to Day 351
- Number of participants receiving 1, 2, etc. maintenance doses prior to Day 351
- Total number of participants with an infusion interruption as well as total number of infusions interrupted from Day 1 to Day 351
- Number of participants switching to q6w dosing between Day 1 and Day 351
- Duration of study participation calculated as the time in days from the date of signing the informed consent to the date of study completion/discontinuation (ie, study duration = date of completion/discontinuation - date of informed consent + 1).
- Total time on study treatment (days) calculated as the time in days from first study drug infusion
 date to the last study drug infusion date (ie, treatment duration=last study drug infusion date first
 study drug infusion date + 1).

By-participant listings of exposure and study duration will be presented.

7.7. Treatment Compliance

The frequency and percentage of participants who had a percentage of drug compliance range by increments of 10% (ie, \geq 100%; \geq 90% to < 100%; \geq 80% to < 90%; etc.) will be calculated for the Safety Set.

This will be calculated as follows:

Percent compliance = total number of study drug infusions administered from Day 1 to study completion or discontinuation / total number of expected infusions from Day 1 to study completion or discontinuation.

Treatment compliance percentage will be summarized for participants diagnosed with or quarantined because of COVID-19 during the study.

A by-participant listing will be produced for treatment compliance.

This document is confidential.

SAP Version: 2.0 09-Feb-2023

Controlled Document ID: 3903A.02, Effective Date 31-Aug-2020

8. Efficacy

This is an estimation study; no formal hypothesis testing will be performed.

8.1. Primary Efficacy Endpoint and Analysis

The primary efficacy endpoint is the proportion of participants who experience free C5-associated BTH through Day 351.

BTH is defined as at least 1 new or worsening symptom or sign of intravascular hemolysis (fatigue, hemoglobinuria, abdominal pain, shortness of breath [dyspnea], anemia [hemoglobin < 10 g/dL], MAVE, including thrombosis, dysphagia, or erectile dysfunction) in the presence of elevated LDH, which is defined as LDH \geq 2 × ULN. The determination about whether a BTH has occurred will be reflected on the BTH form of the eCRF. In the event of a BTH outside the visit schedule, an unscheduled visit will occur, at which point all information pertaining to the BTH will be collected.

Free C5-associated BTH is defined as BTH concurrent with free C5 concentrations $\geq 0.5 \,\mu\text{g/mL}$. The first C5 concentration captured on or after the date of the BTH will be considered when defining a BTH event as free C5-associated.

The proportion of participants who experience free C5-associated BTH through Day 351 will be calculated along with a 2-sided exact 95% CI using the Clopper-Pearson method. All data will be listed.

Participants who withdraw from the study due to lack of efficacy during the Evaluation Period will be considered as non-responders and will be counted in the group with free C5 associated BTH if free C5 is ≥ 0.5 µg/mL at ET visit. For participants who withdraw from the study for any other reason during the Evaluation Period, their data up to the time of withdrawal will be used to assess free C5 associated BTH.

